**Table 4. Median and variability of key endpoints – results of the BORTEJECT study**

Endpoints	All patients	n	Placebo (n=23)	Bortezomib (n=21)
HLA DSA after 1 yr				
Immunodominant DSA	3553 (1012-10365; 163-16284)	39	4360 (1080-10226; 778-16284)	2054 (918-10968; 163-14461)
Sum of DSA MFI	4605 (1119-12009; 273-33855)	39	5410 (1354-13612; 778-28828)	3479 (929-12009; 273-33855)
Follow-up biopsy (24 mo)				
g+ptc score	2 (1-5; 0-6)	38	2 (1-5; 0-6)	4 (0-5; 0-6)
IF/TA score	3 (2-5; 0-6)	38	3 (2-4; 0-6)	3 (2-5; 0-6)
Molecular ABMR score	0.61 (0.30-0.89; 0.05-0.99)	37	0.58 (0.24-0.89; 0.08-0.99)	0.77 (0.41-0.90; 0.05-0.97)
Kidney parameters after 1 yr				
eGFR, ml/min/1.73 m 	44 (23-72; 15-95)	43	53 (23-81; 15-95)	42 (25-69; 15-89)
Protein/creatinine ratio, mg/g	201 (86-1249; 0-4863)	44	194 (82-959; 0-4863)	208 (100-1427; 0-2972)

## 8. INTERIM ANALYSES

This study will be monitored by an independent data and safety monitoring board (DSMB) to assess the safety and data quality. To timely detect major differences between groups in terms of safety aspects, the board members will be instructed to perform interim analyses after 10 and 20 patients have finalized part A of the study. The DSMB will analyze recorded AEs and safety lab results in relation to the randomization sequence. The trial will be terminated prematurely in the following cases: (i) if adverse events occur which are so serious that the risk-benefit ratio is not acceptable, and (ii) if the number of dropouts is so high that proper completion of the trial cannot realistically be expected. For this pilot trial, exact statistical definitions of criteria for premature study termination are not defined.

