### **Blinding and unblinding**

The first part (A) of the study is designed as a double-blinded trial, in order to minimize bias. Investigational drug (clazakizumab) and placebo (normal 0.9% saline) are prepared by non-blinded pharmacists and formulated to have identical appearance. Neither study participants nor medical staff interacting with patients or data know the assigned treatment (clazakizumab versus placebo). The randomization sequence will be unblinded after the last patient has completed the 12-week follow-up period. Premature unblinding may be necessary in cases of medical emergencies or serious medical conditions, where participants cannot be treated adequately unless the medical staff knows the allocated treatment. Unblinding can, if necessary, be requested by the DSMB.

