### Reporting procedures for SAEs

In the event of serious, the investigator has to use all supportive measures for best patient treatment. A written report is also to be prepared and made available to the clinical investigator immediately. The following details should at least be available:

- Patient initials and number
- Patient: date of birth, sex, ethical origin
- The suspected investigational medical product (IMP)
- The adverse event assessed as serious
- Short description of the event and outcome

If applicable, the initial report should be followed by the Follow up report, indicating the outcome of the SAE.

All SAEs for which there is a reasonable possibility the experience may have been caused by clazakizumab (this applies to both expected and unexpected events) will be recorded on a CIOMS Form and submitted to:

SAE Reporting	Contact Information
Vitaeris Drug Safety: [name] This must be reported to Vitaeris within 24 hours.	[contact] (Office), [name] (cell) email: [contact] For submission of SAE report information: By email: [contact] or [contact]

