### Reporting procedures for SUSARs

It must be remembered that the regulatory authorities, and in case of SUSARs which could possibly concern the safety of the study participants, also the Institutional Review Board / Independent Ethics Committee (IRB / IEC) are to be informed. Such reports shall be made by the study management and the following details should be at least available:

- Patient initials and number
- Patient: date of birth, sex, ethical origin
- Name of investigator and investigating site
- Period of administration
- The suspected investigational medical product (IMP)
- The adverse event assessed as serious and unexpected, and for which there is a reasonable suspected causal relationship to the IMP
- Concomitant disease and medication
- Short description of the event:
  - Description
  - Onset and if applicable, end
  - Therapeutic intervention
  - Causal relationship
  - Hospitalization or prolongation of hospitalization
  - Death, life-threatening, persistent or significant disability or incapacity

Electronic reporting should be the expected method for reporting of SUSARs to the competent authority.

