### **The Development Safety Update Report (DSUR)**

The DSUR will be provided by the principal investigator at least once a year.

This report will also be presented annually to the Independent Ethics (IEC) and to the competent authorities by the sponsor.

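### In the available text no reporting route brings serious events to the DSMB outside its two reviews (after 10 and 20 part A completers), and the adverse-event definition, read literally, could leave out death, graft loss and treated rejection

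*Combined protocol and SAP*

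**What the plan says.** Section 8 sets up the board in general terms, "This study will be monitored by an independent data and safety monitoring board (DSMB) to assess the safety and data quality", and then gives its schedule: "the board members will be instructed to perform interim analyses after 10 and 20 patients have finalized part A of the study". At those looks it examines recorded adverse events and safety laboratory results against the randomisation sequence. One of the two grounds for stopping is "if adverse events occur which are so serious that the risk-benefit ratio is not acceptable". Section 11 repeats this ground, and neither section ties it to a scheduled look. The only other mention of the board is in Section 3, Blinding and unblinding: "Unblinding can, if necessary, be requested by the DSMB".

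Section 10 names the recipients of safety reports:

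- SAEs: "A written report is also to be prepared and made available to the clinical investigator immediately". Those with a reasonable possibility of being caused by clazakizumab also go to the supplier: "This must be reported to Vitaeris within 24 hours".
- SUSARs: the bodies to be informed are "the regulatory authorities, and in case of SUSARs which could possibly concern the safety of the study participants, also the Institutional Review Board" or independent ethics committee.
- Annual report (DSUR): "This report will also be presented annually to the Independent Ethics (IEC) and to the competent authorities by the sponsor".

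Section 10 also defines what is reportable. Under Definition of adverse events, the occurrence of a protocol endpoint is listed among the things that are not adverse events, unless defined otherwise. The next subsection defines an SAE as an adverse event that meets at least one seriousness criterion. The outcome table in Section 5 lists one-year graft and patient survival, and biopsy-proven acute rejection needing treatment, as secondary outcomes.

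**The concern.** Safety and tolerability is the primary outcome, and Section 9 states that no clazakizumab data exist in transplant patients on dual or triple immunosuppression. Until the last patient reaches week 12, investigators and patients are blinded, and the board is the only body to which the text assigns a safety review by arm. The stopping criteria are qualitative, so the board has to judge individual cases, and it can judge only those it receives. If the text is followed as written, nothing brings it a case before 10 patients have completed part A, between the two looks, or during the later months of part B.

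The definition raises a second, narrower question. If endpoints are not adverse events, and SAEs are drawn from adverse events, a death, a graft loss or a treated rejection could be missing from the SAE reports, from the events the board analyses, and from the count that forms the primary outcome. In a late antibody-mediated rejection population these are the events a safety board would most want to see.

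**Working it through.** **Reporting routes.** Setting the three Section 10 routes beside Section 8 gives these recipients: the clinical investigator (all SAEs), the supplier (possibly drug-caused SAEs, 24 hours), the authorities and ethics committee (SUSARs), and the ethics committee and authorities (annual report). The DSMB is in none of them. The DSUR sentence says the report is also presented to those bodies, so a further recipient may exist, but none is named.

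**Timing of the reviews.** The plan gives no calendar time for them, so it has to be derived.

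Inputs: 20 patients (Section 3); recruitment of 18 months and trial completion at 30 months (Section 3, Part B); part A of 12 weeks and part B of 40 weeks (Section 3). Assumptions: no dropout, and either even or uniform random accrual.

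The plan's own figure reproduces: 18 + 12 = 30 months.

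18 months = 78.3 weeks. Even spacing s can be taken as 78.3/20 = 3.91 weeks or 78.3/19 = 4.12 weeks.

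- Review 1, from the first dose: 9s + 12 = 47.2 or 49.1 weeks.
- Review 2, from review 1: 10s = 39.1 or 41.2 weeks.
- Review 1 under uniform random accrual: the 10th minus the 1st of 20 uniform entry times, as a fraction of the recruitment period, is Beta(9, 12). So the time is 78.3 × Beta(9, 12) + 12, with median 45.4 weeks and 5th to 95th percentile 32.2 to 59.5 weeks.

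Sensitivity of review 1:

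- Recruitment over 12 months gives 35 to 37 weeks, and over 24 months 59 to 61 weeks (even accrual).
- Poisson accrual at the same rate gives a 5th to 95th percentile of about 30 to 68 weeks.
- The trigger counts completers, so dropout delays it. With an assumed 10% or 20% dropout in part A, the median under uniform accrual moves to about 49 or 54 weeks.

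**Part B time after review 2.** Review 2 falls when the 20th patient reaches week 12. A patient enrolled k places earlier then has max(0, 40 − ks) weeks of part B left. Summing over k = 0 to 19:

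- s = 4.12: ten terms are positive, so 10 × 40 − 45 × 4.12 = about 214.6 patient-weeks.
- s = 3.91: eleven terms are positive, so 11 × 40 − 55 × 3.91 = about 224.8 patient-weeks.

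Part B totals 20 × 40 = 800 patient-weeks, so 26.8% to 28.1% follow the last stated review. By then allocation has been unblinded and all treatment is open-label, so what is missing in that period is independent oversight and not a comparison of arms.

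**Endpoint wording.** No arithmetic applies. Three statements combine: endpoints are not adverse events unless defined otherwise; an SAE is an adverse event of a certain kind; graft and patient survival and treated rejection are endpoints. Taken literally, these events are neither AEs nor SAEs unless another clause brings them back. No clause in the available text does so expressly.

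**The case against.** The strongest objection is that this argues from silence where text is known to be missing. A part of the document between the DSMB paragraph in Section 8 and the start of Section 9 was not available. Section 8 speaks of instructing the board, which suggests separate instructions or a charter. This stands as a limit: the point concerns the available text, and a charter could settle the routing part.

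A reader might infer that the board cannot act between looks. The documents do not support that. It monitors the study in general, the stopping criterion is not tied to a look, and its power to request unblinding comes directly after the sentences on medical emergencies, which suggests that it was expected to hear of individual cases. What is missing is the mechanism.

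A reader might also take the weeks above as delays in detecting or acting on harm. They are times to a scheduled board review only. Adverse events and safety laboratory values are checked at every study visit, Section 9 gives patient-level stopping rules, possibly related SAEs reach the supplier within 24 hours, SUSARs reach the authorities and ethics committee, and the sponsor may close the study at any time. These routes remain in force. They do not provide independent review of unblinded cases across both centres, and an SAE judged unrelated by a blinded investigator has no stated route to an independent reviewer before the next look.

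The early stop of the clazakizumab study in graft-versus-host disease (Section 1) might be read as proof that a board route is needed. It used 160 mg intravenously in another population, and the text does not say that a board stopped it.

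On the endpoint wording, the literal reading is probably not intended. Safety is itself the primary endpoint, death is listed as a seriousness criterion, worsening of existing disease counts as an adverse event, and Section 7 analyses graft and patient survival separately, so these events would not vanish from the trial report. That makes the wording an ambiguity, and the document does not say that deaths or graft losses will go unreported as SAEs.

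**Conclusion.** The point holds for the available text. The only stated DSMB safety reviews come after 10 and 20 part A completers, and no SAE, SUSAR or DSUR route names the board. The gap covers the time before the first review, the interval between the two, and more than a quarter of part B time after the second. The calendar figures rest on 20 patients over 18 months without dropout; slower recruitment or dropout would push the first review later, and faster recruitment would bring it forward.

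The endpoint clause is a separate ambiguity, and it affects both the board's material and the primary safety count. A charter that already routes events to the board might still leave it open.

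No event rate and no actual delay in action is claimed, because the documents give no SAE rate for this population. No extra formal comparison of arms is proposed. The point is worth acting on because safety is the primary outcome in a population without prior data and the remedy is small.

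**What to change.** 1. In Section 10, add a sentence: death, graft loss and treated rejection are recorded and reported as AEs or SAEs even though they are also study endpoints.
2. In Sections 8 and 10, copy SAEs to the existing DSMB on an expedited clock. The 24 hours already used for the supplier is a natural choice, although that clock now covers only possibly drug-caused events. Make part A allocation available to the board through a closed channel so that site staff stay blinded.
3. In Section 8, name a short list of sentinel events, agreed with the board, that prompt an unscheduled review in part A or part B. Candidates are death, graft loss, gastrointestinal perforation and anaphylaxis. The board and sponsor should settle the list and what follows from a review.

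If a charter already provides items 2 and 3, cite it in Section 8; item 1 is then the only new text needed.

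The cost is a few sentences of amendment, some extra SAE forwarding, a closed channel for allocation, and possibly one or two extra board calls. The scheduled looks, visits and sample size do not change.

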## 9. ADVERSE DRUG REACTIONS

### Clazakizumab

From previous studies, results obtained in approximately 900 clazakizumab-treated patients/subjects are available for assessment of safety patterns. Overall, adverse events (AEs) reported for clazakizumab treatment are consistent with IL-6 blockade. In previous studies, e.g. in RA and PsA, clazakizumab was administered at doses up to 320 mg, and many patients have received this antibody as an add-on to treatment with methotrexate. However, until now, no data obtained in transplant patients on dual or triple immunosuppression are available, so that safety assessment remains a major objective of this pilot trial. However, preliminary data obtained with the IL-6R antibody tocilizumab in transplant recipients point to a beneficial safety profile of targeting of IL-6/IL-6R also in patients on calcineurin inhibitor (CNI)-based immunosuppression.

Reported AEs caused by clazakizumab are abnormalities in liver function parameters, which are commonly mild to moderate in severity [ $<3 \times$  upper limit of normal (ULN) in most cases] and were more frequent under concomitant methotrexate treatment. Clinically significant increases in liver function parameters were shown to occur only in a few patients. Clazakizumab was shown to decrease neutrophil counts, whereby the majority of observed cases were mild/moderate in severity, without clinical sequelae. In phase 2 studies evaluating clazakizumab in arthritis, reported infection rates under repeated administration of clazakizumab were low and comparable to patients allocated to control groups. Nevertheless, intensified immunosuppression, in addition to standard dual or triple baseline

immunosuppression, can be expected to be associated with an increased infection risk. Hence, a careful patient follow-up will include a close monitoring for infectious complications (bacterial, viral and fungal infections). In trials of arthritis, no case of gastrointestinal perforation was reported. However, given the low, but significantly increased risk of gastrointestinal perforation in other large studies evaluating IL-6/IL-6R blockers, patients with a history of gastrointestinal perforation, diverticulitis or inflammatory bowel disease will not be included in the trial. Clazakizumab, as other agents interfering with IL-6/IL-6R, was shown to increase total cholesterol and LDL levels. Moreover, in some patients, a mild decrease in platelet counts was observed. Serious infusion reactions have not been described in any of the published trials, but clazakizumab may cause injection site reactions, apparently in a dose-dependent fashion. Safety results obtained for prolonged treatment with subcutaneous clazakizumab at 25 mg (with or without methotrexate) in two recent phase 2 trials, one in RA, the other in PsA, are summarized in Table 5 (in both trials also higher doses of clazakizumab were evaluated; some events, such as injection site reactions or liver enzyme elevations, were thereby more frequently observed at higher dosages).

**Table 5. Summary of AEs reported for clazakizumab at 25 mg - phase 2 trials in arthritis**

Disease entity Author, year	Psoriatic arthritis Mease et al, 2016 		Rheumatoid arthritis Weinblatt et al, 2015 	
	Placebo ±MTX	Clazakizumab 25 mg ±MTX	Placebo +MTX	Clazakizumab 25 mg +MTX
Patient number	41	41	61	59
Deaths	0%	0%	0%	0%
GI perforations	0%	0%	0%	0%
Malignancies	0%	0%	0%	0%
SAEs	4.9%	4.9%	3.3%	8.5%
Discontinuation (SAEs)	4.9%	0%	0%	0%
AEs	65.9%	73.2%	60.7%	84.7%
Discontinuation (AEs)	7.3%	2.4%	0%	0%
Infections	48.8%	36.6%	total infection rate not reported	
Liver parameters				
ALT >1-3 x ULN	24.2%	52.6%	21.6%	46%
ALT >3-5 x ULN	0%	5.3%	2%	3.7%
ALT >5-8 x ULN	2.0%	0%	0%	3.7%
AST >1-3 x ULN	13.5%	50%	14.8%	40%
AST >3-5 x ULN	0%	0%	0%	3.6%
AST >5-8 x ULN	0%	2.6%	0%	0%
Total bilirubin				
>1.0-1.5 x ULN	0%	10.8%	0%	8.8%
>1.5-2.0 x ULN	0%	5.4%	0%	1.8%
>2.0-3.0 x ULN	0%	2.7%	0%	0%
Cases of Hy's law	0%	0%	0%	0%
Lipids				
LDL	no details (lipids elevated)		Increase from <130 to ≥130 mg/dL	
			28.3%	61.9%
Neutrophil counts	Mean decrease by about 2 G/L			
0.5-1.0 x 10  /liter	no details		0%	1.8%
1.0-1.5 x 10  /liter	no details		3.8%	14.3%
Anti-clazakizumab Ab	-	4.9%	-	5.1%
Injection site reaction	-	9.8%	-	13.6%

## Adverse drug reactions - specific considerations

### *Opportunistic Infections and Serious Infections*

Physicians should exercise caution when considering the use of clazakizumab in patients with a history of recurring infection or with underlying conditions (eg, diabetes) which may predispose patients to infections. Clazakizumab should not be administered in patients with active infection. The effects of clazakizumab on CRP, neutrophils, and the signs and symptoms of infection should be considered when evaluating a patient for a potential infection.

Vigilance for timely detection of serious infection is recommended for transplant patients receiving biologic agents as signs and symptoms of acute inflammation may be lessened due to suppression of the acute phase reaction. Patients must be instructed to contact their physician immediately when any symptoms suggesting infection appear, in order to assure rapid evaluation and appropriate treatment.

If a patient develops a serious infection, administration of clazakizumab is to be interrupted until the infection is controlled. The clinician should consider the benefit-risk before resuming treatment with clazakizumab.

**Gastrointestinal Perforations**

Timely diagnosis and appropriate treatment may reduce the potential for complications of diverticulitis and thus reduce the risk of GI perforations. Therefore, patients should be made aware of the symptomatology potentially indicative of diverticular disease, and they should be instructed to alert their healthcare provider as soon as possible if these symptoms arise. In patients with a history of symptomatic diverticulosis, diverticulitis or chronic ulcerative lower GI disease such as Crohn’s disease, ulcerative colitis or other chronic lower GI conditions that might predispose to perforations, the clinician should consider the benefit-risk before using clazakizumab. Discontinuation of clazakizumab is necessary for patients who develop GI perforations.

**Hematologic Abnormalities and Bleeding Events**

Decreases in neutrophil and platelet counts have been observed following treatment with clazakizumab in combination with MTX. In addition, there may be an increased risk of neutropenia in patients who have previously been treated with a TNF antagonist. For patients with concomitant medications associated with hematologic toxicity, the reduction or interruption of the suspected medication is recommended prior to modifying clazakizumab. Dosing guidance for neutropenia and thrombocytopenia are described in Tables 6 and 7.

**Table 6. Neutropenia risk mitigation**

ANC (cells/mm  )	Action
> 1000	Maintain dose.
500 – 1000	Interrupt clazakizumab dosing. When ANC increases to > 1000, resume clazakizumab 25mg SQ monthly
< 500	Discontinue clazakizumab.
ANC = absolute neutrophil count	

**Table 7. Thrombocytopenia risk mitigation**

Platelet count (cells/mm  )	Action
> 100,000	Maintain dose.
50,000 – 100,000	Interrupt clazakizumab dosing. When platelet count increases to > 100,000, resume Clazakizumab at 25mg SQ monthly
< 50,000	Discontinue clazakizumab.

Dosing recommendations for events of elevated liver enzymes are described in Table 8.

### ***Elevated Liver Enzymes and Hepatic Events***

Elevations in ALT and AST have been observed during treatment with the study medications

**Table 8. Elevated liver enzymes – risk mitigation**

Lab Value	Action
> 1 to 3x ULN	Dose modify concomitant transplant immunosuppressive drugs if appropriate For persistent increases in this range, interrupt clazakizumab until ALT/AST have normalized Restart with 25mg SC monthly as clinically appropriate
> 3 to 5x ULN (confirmed by repeat testing)	Interrupt clazakizumab dosing until < 3x ULN and follow recommendations above for >1 to 3x ULN For persistent increases > 3x ULN, discontinue clazakizumab Discontinue clazakizumab if total bilirubin >2 x ULN
> 5x ULN	Discontinue clazakizumab

### ***Cardiovascular Events and Elevated Lipids***

Kidney transplant recipients may have an increased risk for cardiovascular disorders, therefore, risk factors for cardiovascular disease (eg, hypertension, hyperlipidemia) should be managed as part of their standard of care. See section on Drug Interactions.

For patients with LDL cholesterol  $\geq 160$  mg/dL, it is strongly recommended that investigators advise therapeutic lifestyle changes that may include initiation lipid-lowering agents. Lipid-lowering agents should also be considered for patients with lower LDL cholesterol levels as part of their therapeutic lifestyle changes depending on their overall risk as defined in NCEP ATP III or other national guidelines.

